4.3 Handling of Missing Data

All missing or partial data will be presented in the subject data listing as they are recorded on the case report form (CRF) including best estimate dates of site investigators collected in the clinical database.

Missing or incomplete post-randomization event dates

All efforts will be made to collect complete data for all subjects randomized in this study including visits by telephone contact. Subjects will be followed to the study end and all required data will be collected, regardless of their compliance with study medications or visits.

When an event date is not complete, the date will be estimated according to the following rules but not earlier than randomization date,

- If only the onset day is missing, but the month and year are available:
 - If the month and year are the same as the efficacy cut-off date (ECOD), impute the date as mean of the first day of the onset month/year and the ECOD (rounded up).
 - Otherwise if the month and year are the same as the last contact date alive (see [Appendix A](#)), impute the date as mean of the first day of the onset month/year and the last contact date alive (rounded up). For death event, the last contact alive date +1 day will be used as the death date.
 - Otherwise impute the event date as maximum of the date of randomization + 1 and day 15 of the onset month and year.
- If the onset day and month is missing, but the year available:
 - The minimum possible date is maximum of randomization date + 1 days and January 1st of the onset year.
 - The maximum possible date is the minimum of the ECOD and last contact date alive and December 31th of the onset year.
 - Impute the event date as mean of the minimum possible date and the maximum possible date (rounded up).
 - For subjects who experienced death in the same year as last contact alive date, the last contact alive date +1 day will be used as the death date.
- If the onset date is complete missing, the onset date will be imputed with the randomization date + 1 days.
- For subjects who experienced death during the study and the death date is completely missing, the last contact alive date + 1 day will be used to impute death date. If the last contact alive date is missing, the death date will be imputed as ECOD.

Statistical Analysis Plan

Protocol No.: **BAY 59-7939 / 17454**

Page: 10 of 36

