4.5.2 Data Scopes

All analyses are based on two elements:

- 1) *analysis set*, which specifies which subjects will be included in an analysis; and
- 2) *data scope*, which specifies the time window within which data will be included in an analysis.

This section describes the coverage of the event *data scopes* used for the statistical analyses. *Analysis sets* are described in Section 5.

Data scope according to intention-to-treat principle (ITT)

The ITT data scope includes outcome events observed from randomization date until the ECOD. Events occurring after the ECOD will not be counted for primary analysis. This ITT data scope will be applied mainly to the analyses of efficacy variables.

Data scope according to treatment (on-treatment)

The on-treatment data scope will include all outcome events observed from randomization until 2 days following permanent discontinuation of the study drug. This on-treatment data scope will be applied mainly to the analyses of safety variables (e.g. bleeding).

Data scope according to overall study duration for sensitivity analysis

The overall study duration data scope will include all outcome events observed from randomization until the last contact/visit. This data scope will be applied for sensitivity analysis only.

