4.5.3 Censoring rules for time-to-event variables

All efforts will be made to collect complete data for all subjects randomized in this study including visits by telephone contact.

Censoring rules for analyses according to the ITT principle

The censoring rule for time to first event analyses depends on the type of endpoint, thereby distinguishing between clinical events endpoints (primary efficacy composite and component, secondary efficacy and bleeding events) and CV-death / all-cause mortality.

Statistical Analysis Plan

Protocol No.: **BAY 59-7939 / 17454**

Page: 12 of 36

	Primary efficacy composite and components other than CV-death	All-cause mortality, CV-death
If the subject was randomized but has no post-randomization clinical event ascertainment date the subject will be censored :	At the randomization date + 1 day	Earlier of last contact alive date or ECOD If no last contact alive date, use the randomization date +1 day
Else, if the subject has withdrawn from the study but objected to further data collection the subject will be censored :	At the earlier date of the last clinical event ascertainment date (LCEAD), date of objection to further data collection or ECOD	Earlier of last contact alive date from public sources or ECOD If no last contact alive date from public sources, use the earlier date objection to further data collection or ECOD
Otherwise, the subject will be censored :	At the earlier date of last clinical event ascertainment date, date when patient died or ECOD	At the earlier date of last contact alive date or ECOD

Censoring rules for analyses according to the on-treatment principle

For on-treatment analyses (primary analysis for time to bleeding events, sensitivity analysis for primary efficacy endpoint and all secondary efficacy endpoints), patient with at least one dose of study medication and without documentation of an event within the on-treatment data scope will be censored similarly to the ITT data scope except that the date of last dose of study treatment + 2 days will be used as the cap for the time scope instead of ECOD.

Censoring rules for analyses according to the overall study duration principle

Above censoring rules for ITT data scope apply except that the date of last clinical event ascertainment or last contact alive will be used as the cap for the time scope instead of ECOD.

See [Appendix A](#) for additional details.

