6.4 Safety

6.4.1 Adverse events

Because the safety profile of rivaroxaban has been well established in previous large and extensive trials, this study will collect limited AE data. Adverse events (AEs) will be coded by Medical Dictionary for Regulatory Activities (MedDRA). The version number of MedDRA used for the analyses will be stored in the clinical database. A listing will be provided linking the original investigator terms and the coded terms.

Analyses of reported adverse events will be performed based on the SAF and on-treatment data scope.

In case of uncertainty (e.g., missing or incomplete dates), AEs will be classified as “treatment emergent” (TE) following the worst case approach.

An overall summary of AEs and treatment-emergent (TE) AEs (only considering study medication of rivaroxaban or rivaroxaban placebo) will be generated by treatment group and overall.

Incidence of subjects with treatment emergent adverse events (TEAEs), drug-related and/or serious TEAEs, and TEAEs causing discontinuation of study drug will be summarized by treatment grouped by MedDRA Primary System Organ Class (SOC) and Preferred Term (PT). In addition, the incidence of pre-treatment AEs and AEs during the post study treatment follow up will be tabulated.

Serious adverse events (SAEs), AEs leading to discontinuation and AEs of special safety interest (if applicable) will be listed. The date, relative day (to start of study medication) and phase of the study (pre-treatment, during treatment, post-treatment) will be included.

Further summaries of AEs by maximum intensity and worst outcome will be provided, consistent with Bayer Global Medical Standards.

Specific to Japan, outcome events (i.e. bleeding, efficacy outcome events) are reported as an (S)AEs as required by PMDA, thus (TE)AEs and SAEs will be further presented for Japan only subjects vs. non-Japan subjects.

Statistical Analysis Plan

Protocol No.: **BAY 59-7939 / 17454**

Page: 27 of 36

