6.4.5 Analysis of safety variables

The analysis of the primary and secondary safety variables will be based on the SAF and on-treatment data scope.

Time to the first occurrence of the primary safety endpoint (i.e., TIMI major bleeding) will be compared using a Cox proportional hazards model stratified by type of procedure and use of clopidogrel (per IxRS assignment) with treatment group as a covariate. A plot of cumulative event rate derived by Kaplan-Meier estimate will be provided to show event rate and treatment effect by time.

The secondary safety outcome variables will be analyzed similarly.

As supportive analyses, the primary safety variable will be analyzed as described above based on the SAF and ITT data scope as well as overall study duration including post-study treatment follow-up. In addition, the primary safety variable will be analyzed according to the actual qualifying revascularization procedure (section 6.2.9) and in subgroups as described in section 6.2.4. Number of subjects with multiple TIMI major bleedings will also be summarized in frequency table.

As exploratory analyses, landmark analysis similar to those as described in section 6.2.8 will also be performed for the primary safety variable.

Additionally number of patients with bleeding leading to permanent drug discontinuation will be summarized by bleeding sites.

Concordance of ICAC and investigator reports on the TIMI major bleeding events will be provided for the combined treatment group.

Other safety variables will be summarized descriptively.

Any pregnancy occurring in a study subject during the subject's participation in this study will be displayed.

Statistical Analysis Plan

Protocol No.: **BAY 59-7939 / 17454**

Page: 28 of 36

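### SAP 4.3 imputes partial bleed dates without regard to the last dose, so a month-only bleed that ended treatment early in a month is left out of the main on-treatment bleeding analysis (minor)

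*SAP*

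**What the plan says.** **Date imputation.** SAP 4.3 has one set of rules for incomplete post-randomization event dates. With only the day missing, three branches apply in order:

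- Cut-off (ECOD) month: "If the month and year are the same as the efficacy cut-off date (ECOD), impute the date as mean of the first day", with the ECOD as the other end of the midpoint.
- Last-contact month: "Otherwise if the month and year are the same as the last contact date alive", the midpoint of the first of the month and that contact date.
- Any other month: "Otherwise impute the event date as maximum of the date of randomization + 1 and day 15 of the onset month and year".

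A year-only date goes to the middle of the possible range, and a wholly missing date goes to the day after randomization. The last-dose date appears in none of these rules.

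**Window for bleeding.** SAP 6.4.5 and Table 1 base the main analysis of TIMI major, ISTH major and BARC 3b-and-above bleeding on the safety set and the on-treatment scope. Under SAP 4.5.2, "The on-treatment data scope will include all outcome events observed from randomization until 2 days following permanent discontinuation of the study drug". For censoring, SAP 4.5.3 says that "the date of last dose of study treatment + 2 days will be used as the cap for the time scope instead of ECOD".

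**Adverse events are handled differently.** SAP 6.4.1 states: "In case of uncertainty (e.g., missing or incomplete dates), AEs will be classified as" treatment emergent, on a worst-case basis. Protocol 9.6.1.3.1 and 9.6.1.3.3 exempt bleeds from AE recording, so this protection does not reach the time-to-bleeding analyses. (In Japan outcome events are also reported as AEs, but that affects only the AE tables.)

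**Protocol rule.** Protocol 10.3.3.5 takes the middle of the period in which the event is known to have happened.

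**The concern.** The imputation rule and the analysis window are set independently of each other, yet the first decides whether an event falls inside the second. The bleeds exposed to this are those that made the patient stop study drug, which are the ones most plausibly related to treatment. Such a patient would be censored event-free at last dose + 2 days in the primary safety analysis of an anticoagulant trial.

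Two inconsistencies follow. SAP 6.4.5 also promises that the "number of patients with bleeding leading to permanent drug discontinuation will be summarized by bleeding sites", so that table could include a patient whom the main analysis treats as having had no bleed. And a bleed with no date at all is placed on the day after randomization, normally inside the window, while a bleed known to have occurred in a given month can fall outside it. Knowing more about the date should not remove the event.

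**Working it through.** The plan gives no figure for partial bleed dates, so there is nothing of its own to reproduce. The check compares the rule with the window.

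**Inputs.** Imputed day 15 in an ordinary month (SAP 4.3). Window end at last dose + 2 days (SAP 4.5.2, 4.5.3). Bleed and last dose in the same month, last-dose day *d* known, bleed day missing.

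**1. When the bleed is lost.** It is dated off-treatment if 15 > *d* + 2, that is, if *d* ≤ 12. Example: a bleed recorded only as May leads to permanent discontinuation with last dose on 5 May. The window closes on 7 May, the bleed is dated 15 May, and it is not counted. With *d* = 13 or later it is kept.

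**2. Share of last-dose days affected (assumed uniform over the month).**
- 31-day month: 12/31 = 38.7%
- 30-day month: 12/30 = 40.0%
- 28-day month: 12/28 = 42.9%
- Two full non-leap years: 24 × 12 / 730 = 288/730 = 39.5%

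This assumes that stopping follows the bleed at once. Any delay moves the last dose later in the month or into the next one, where the bleed is kept, so about 39% is close to an upper bound.

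**3. The other branches.** The midpoint day is 1 + (L − 1)/2, rounded up, where L is the day of the ECOD or of last contact alive.
- L = 10: imputed day 6, lost if *d* ≤ 3
- L = 20: imputed day 11, lost if *d* ≤ 8
- L = 30: imputed day 16, lost if *d* ≤ 13

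The loss remains, with a different threshold.

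**4. When the loss does not occur.** If the last-dose day is also missing, SAP Appendix D normally sets it to the end of the month, and the bleed is kept.

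**5. The opposite error.** Take all 30 × 30 pairs of true bleed day and last-dose day in a 30-day month as equally likely, for bleeds unrelated to stopping. Then 522 pairs are truly on-treatment, of which 102 (19.5%) are dated out; 378 are truly off-treatment, of which 120 (31.7%) are dated in. In general the rule errs both ways. For a bleed that itself ended treatment, the error is essentially always a loss.

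**6. Protocol rule on the same example.** If the bleed is known to have preceded the last dose on 5 May, the known period is 1 to 5 May and its middle is (1 + 5)/2 = 3 May, inside the window. SAP 4.3 does not carry this bound over.

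**7. Overall size (assumed inputs).** Let 1–5% of bleeds have partial dates and 20–40% of those end treatment. Neither range is in the documents.
- Low: 0.01 × 0.20 × 0.39 = 0.08%
- High: 0.05 × 0.40 × 0.39 = 0.78% of on-treatment bleeds

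With a cap at last dose + 2 days for bleeds that ended treatment, 0 of 30 last-dose days lose the bleed, against 12 of 30 as written.

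**The case against.** The best case for leaving the text alone is that this combination should hardly ever arise. A site that knows the patient stopped on 5 May because of a bleed can usually date the bleed. Potential major bleeds go to adjudication with a compiled package, and SAP Appendix A refers to adjudicated event start dates. SAP 4.3 also describes the recorded data as "including best estimate dates of site investigators collected in the clinical database". The 1–5% and 20–40% inputs are guesses, and multiplying them treats partial dating and stopping as independent, although bleeds that stop treatment are likely to be the best dated. TIMI major bleeding is re-analysed under the ITT scope and over the whole study duration, so a material loss would show as a discrepancy. The rule is the same in both blinded arms, and mid-period imputation is the protocol's own principle.

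Most of this stands, and it limits the size of the problem. A reader might infer that SAP 4.3 ignores investigators' best-estimate dates. The documents do not support that: imputation starts only when a date is incomplete, so a complete best estimate may never reach these rules. What does not stand is the view that nothing needs changing. Once imputation is triggered, the stated rule puts a bleed that ended treatment after the end of treatment. The supportive analyses keep that event but do not correct the main estimate, and Table 1 lists none for ISTH major or BARC 3b-and-above bleeding.

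**Conclusion.** The point holds and is minor. In the situation defined in steps 1 and 2, the SAP's own text drops a bleed that led to permanent discontinuation from the main safety analysis. A TIMI major bleed still counts over the whole study duration and, if dated by the ECOD, in the ITT scope.

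The number affected cannot be computed from the documents. It is probably very small: well under 1% of on-treatment bleeds on the assumed inputs, which are likely to be generous.

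Two stronger readings go too far. One is that the rule understates bleeding overall: it also brings some post-treatment bleeds into the window, and the documents give no basis for netting the two. The other is that the hazard ratio is biased: that would require bleeds with partial dates to end treatment more often in one arm, which is possible but not shown. Nothing here suggests that the safety conclusion would change.

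**What to change.** Add to SAP 4.3, for the bleeding analyses only:

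1. Use the adjudicated onset date or the investigator's best-estimate date where one exists.
2. If the onset date is still incomplete and the bleed is recorded as the reason for permanent discontinuation, cap the imputed date at last dose + 2 days, but not before randomization.
3. For other bleeds whose onset month is known and overlaps the on-treatment window, apply the worst-case approach of SAP 6.4.1 and count them as on-treatment.

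Do not extend this to year-only bleeds unrelated to stopping: someone who stopped in January would have most of that year's possible dates counted as on-treatment. Do not extend it to the on-treatment efficacy analyses either, where worst case for safety has no such meaning.

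The cost is a few sentences and a small programming change. The downside is that a few bleeds that truly came after stopping may be counted as on-treatment. On the grid in step 5, item 3 would count all 120 + 258 = 378 truly off-treatment pairs instead of 120. Those are shares of a very small group of bleeds, and the error is in the conservative direction for safety.

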### **9.2.1.3 Treatment phase: Regular study visits from Visit 1 onwards - amended**

Patients will return to the study site for the first on-treatment visit one month following randomization (Visit 1, with a permitted time window of  $\pm$  10 days). Further regular treatment visits (all with a permitted time window of  $\pm$  4 weeks) will be performed 3 months (Visit 2), 6 months (Visit 3), and 12 months (Visit 4) after randomization, and then every 6 months until the study end will be announced (see Table 9-1).

At each on-site visit in the treatment phase, patients will be asked about the occurrence of potential study efficacy outcome events, bleeding events, and AEs/SAEs. If a suspected study efficacy outcome event or bleeding event is reported, the respective eCRF page will be completed and an adjudication package expeditiously compiled and submitted to the ICAC.

The following measures/documentations will be performed at each study visit:

- check for the occurrence of study efficacy outcome events since the last study visit;
- check for the occurrence of bleeding events since the last study visit;

---

 Last sentence added with Protocol Amendment 4 (change no. 12).

- complete all eCRF outcome event, bleeding event and Health Care Resource Utilization (HCRU see Section 9.7.3) pages if applicable
- check for the occurrence of AEs/SAEs since the last study visit (for events exempted from AE/SAE reporting, see Section 9.6.1.3);
- document any changes in concomitant medications since the last study visit;
- assess the patient's PAD Symptom Status;
- If the following laboratory evaluations have been performed since the last study visit and are available in the medical record, it is requested that this information be recorded in the eCRF: HbA1c, creatinine, total cholesterol, HDL cholesterol, LDL cholesterol, ALT(SGPT), AST(SGOT), total bilirubin, hemoglobin, hematocrit, platelet count;
- QoL assessment with EQ-5D (questionnaires should be completed before the other visit procedures);
- Walking Impairment Questionnaire (questionnaires should be completed before the other visit procedures);
- assess vital signs (blood pressure, pulse rate);
- perform ABI (or TBI);
- collect study medication and study ASA bottles dispensed at the previous visit and count and document number of returned tablets. Document any treatment interruptions, if applicable;

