### 10.3.3.5 Handling of missing data

All efforts will be made to collect complete data for all patients randomized in this study including visits by telephone contact. Patients will be followed to the study end and all required data will be collected, regardless of their compliance with study medications or visits.

When an event date is not complete, the date will be estimated to be the middle date within the period that the event is known to have occurred, e.g., if the event is known to have occurred in the first week of a month, then the date in the middle of that week will be used; if no information is known then the date in the middle of the plausible time period will be used, based on the last contact with the patient prior to the event and the date of contact when information about the event was known.

If a patient experiences a fatal event that is not part of a specific endpoint under analysis, the patient will be considered as having been censored at the earlier date of efficacy cut-off or the time of death. If a patient is lost to follow-up or has withdrawn consent and has not experienced any endpoint events under analysis, the patient will be counted as censored at the last contact date prior to the date of efficacy cut-off, with complete information of the endpoint being analyzed (e.g., for analysis of the primary endpoint, information regarding all components of the primary endpoint need to be available at the contact date).

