In addition, ABI and TBI will be further explored to understand the effect of natural history and drug effect on hemodynamics. Examples include:

- Change in ABI and TBI post randomization excluding values after subsequent revascularization by subgroup (endovascular versus surgical)
- Change in ABI and TBI post randomization in patients with subsequent intervention versus those who do not undergo subsequent intervention

To explore the robustness of the treatment effect over time, landmark analyses will be performed for the primary endpoint according to landmark periods of randomization to 3-month, 3-month to 1-year and 1-year to the end of treatment phase and randomization to 6-month, 6-month to 1 year and 1-year to end of treatment phase ([Van Houwelingen 2007](#)). Additional time point after 1-year may be added depending on the actual study duration. For each landmark period, the hazard ratio will be estimated using a Cox PH model stratified by type of procedure and use of clopidogrel (per IxRS assignment) with treatment as the only covariate, the corresponding 95% CI will be provided, and Kaplan-Meier (KM) plot of cumulative risk will be generated, respectively. The hazard ratio will also be calculated for the two main components (MACE versus MALE) of the primary endpoint.

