		
section 4.5.1, 4.5.3 and Appendix A
 
 Added a few more subgroup variables in section 6.2.4 Added more exploratory analyses (e.g. MACE/MALE endpoints, landmark analysis for primary efficacy endpoint) in section 6.2.8 Added more sensitivity analyses of primary and secondary efficacy endpoints in section 6.2.10 Added AEs analyses for Japan vs. non-Japan patients in section 6.4.1, and supportive analyses in section 6.4.5. Updated benefit/risk analysis in section 6.6 Added Appendix B for the definition of regions Added Appendix C to describe the mathematical details of the tipping point analysis
Version 3.0	24 July 2019	
None of the edits in this SAP version is considered to change the primary efficacy analysis and other analyses as described in the SAP version 2.0, but includes further clarifications and additional analyses.
 
Editorial, administrative, and typographical corrections were made that do not affect the overall SAP. These changes are not described in this section.
 
The following changes are introduced in SAP version 3.0:
 
 Added information on imputation rules for the missing or incomplete post-randomization event dates in section 4.3 Added information on derivation of the first dose and last dose date of study treatment in section 4.5.1. Added analysis in data scopes with overall study duration for sensitivity analysis in section 4.5.2 Added information on censoring rules for efficacy endpoints in section 4.5.3 and

Statistical Analysis Plan

Version	Date	Action

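### A non-fatal event with no date at all is dated to the day after randomization in SAP 4.3, against the protocol's midpoint rule, and the departure is not declared

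*SAP*

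**What the plan says.** Protocol 10.3.3.5 covers an event about whose date nothing is known: "if no information is known then the date in the middle of the plausible time period will be used". It bounds that period by the last contact before the event and the contact at which the event came to light.

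SAP 4.3 gives its own rules by how much of the date is missing:

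- If only the year is known, it takes the mean of the earliest and latest possible dates, which is a midpoint.
- If nothing is known, the rule is "If the onset date is complete missing, the onset date will be imputed with the randomization date + 1 days".
- A completely undated death has a separate rule, "the last contact alive date + 1 day will be used to impute death date", so the day-after-randomization rule governs non-fatal events.

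The same section notes that the database holds "best estimate dates of site investigators collected in the clinical database", so a completely missing date should be a last resort.

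SAP section 7, version 3.0, describes the change as "Added information on imputation rules for the missing or incomplete post-randomization event dates in section 4.3". It adds that none of the version 3.0 edits is considered to change the analyses described in SAP version 2.0. It does not mention the protocol's midpoint rule.

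**The concern.** At every treatment-phase visit, sites must "check for the occurrence of study efficacy outcome events since the last study visit" (protocol 9.2.1.3). An undated event learned of late in follow-up therefore usually has event-free visits before it. Dating it to the day after randomization contradicts those records. The SAP also treats less information as if it pointed to an earlier date: year known gives a midpoint, nothing known gives almost the earliest date possible.

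Three classifications then follow from the rule and not from the data:

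- **Efficacy cut-off date (ECOD).** The event always counts before it, even if first learned of at an end-of-treatment visit held after it.
- **Landmark analyses.** SAP 6.2.8 uses "landmark periods of randomization to 3-month, 3-month to 1-year and 1-year to the end of treatment phase", plus a second set starting with 0–6 months, and SAP 6.4.5 repeats the approach for TIMI major bleeding. The event always falls in the first period.
- **On-treatment scope.** This runs to 2 days after permanent discontinuation (SAP 4.5.2) and is the main scope for bleeding. In a treated patient the day after randomization always lies inside it, so an undated bleed counts as on-treatment even if the drug had been stopped.

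Protocol 10.1 lets the SAP be more technical and detailed. That does not extend to replacing a rule the protocol already sets.

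**Working it through.** **1. Size of the date difference.** Take nominal visits (months 1, 3, 6, 12, then every 6) as the contacts. For an event between contacts at months a and b, the midpoint is later than the SAP date by (a + b)/2 × 30.4375 − 1 days.

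| Window (months) | Difference (days) |
|---|---|
| 0–1 | 14 |
| 3–6 | 136 |
| 6–12 | 273 |
| 12–18 | 15 × 30.4375 − 1 ≈ 456 |
| 36–42 | 1,186 |

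In the 12–18 case the SAP date precedes four event-free visits (months 1, 3, 6 and 12).

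**2. The plan's own figure.** The point does not touch the 1,015 events or the 90% power; they set the scale. Schoenfeld's formula for HR 0.80, one-sided 0.025 and 90% power gives 845 events without allowance for discontinuation. A Markov log-rank model with the plan's discontinuation, loss and accrual inputs and 6,500 patients gives 1,019 events and 90.0% power when 7.5% is read as a hazard. Read as a yearly probability, it gives 1,055 events and 91.0%. The plan's figure reproduces.

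**3. Effect on the primary hazard ratio and the first landmark period.** Inputs from protocol 10.4 and SAP 4.6: 3,250 per arm, control hazard −ln(0.925) per year, HR 0.8, accrual 15/30/55% over 18 months, 24 months after the last patient, 1.5% loss per year. Assumptions: k = 1, 5 or 10 undated events (about 0.1% to 1% of 1,015) drawn at random from all events; every visit attended; unstratified Cox model; no dilution from discontinuation; 800 trials per setting. Because protocol 10.4 expects higher early rates, a doubled hazard in months 0–3 was also run.

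| Hazard | k | 97.5th percentile of absolute HR shift | 0–3 month events, true dates → SAP rule |
|---|---|---|---|
| Constant (about 1,042 events) | 1 | 0.0003 | 112.9 → 113.8 |
| | 5 | 0.0007 | 113.0 → 117.5 |
| | 10 | 0.0011 | 113.5 → 122.4 |
| Doubled early (about 1,136 events) | 1 | 0.0003 | 223.7 → 224.5 |
| | 5 | 0.0008 | 224.0 → 228.1 |
| | 10 | 0.0012 | 223.2 → 231.2 |

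- The mean HR shift is at most 0.00004 in size.
- The 0–3 month count rises by 0.8% to 7.8% (constant) or 0.4% to 3.6% (doubled).
- The 0–3 month HR changes by at most 0.004 on average.
- The true date lies after the month 1 visit in 93–97% of undated events and after month 3 in 80–89%.
- Under the midpoint rule the 97.5th percentile of the absolute HR shift is at most 0.00012.

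**4. Kaplan-Meier at 3 months.** Overstatement = k × share truly after month 3 / 6,500. This runs from 1 × 0.80/6,500 = 0.012 to 10 × 0.89/6,500 = 0.137 percentage points.

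**5. Imbalanced missingness.** The documents give no mechanism for it. With 0.5% of events undated in one arm and 1.5% in the other, the HR moves by 0.0007 (constant) or 0.0008 (doubled). With 2% and 5%, it moves by 0.0021 or 0.0023.

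**6. On-treatment bleeds.** With the plan's discontinuation rates (2,000,000 simulated patients, mean follow-up 30.6 months), 8.3% of follow-up is off drug. Among undated bleeds, the share truly outside the scope but counted as on-treatment by the SAP rule depends on the assumed bleeding rate off drug relative to on drug:

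| Off/on rate | SAP rule misclassifies | Midpoint misclassifies |
|---|---|---|
| 1 | 8.3% | 0.8% |
| 0.5 | 4.3% | 0.6% |
| 0.25 | 2.2% | 0.5% |

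There is one exception. If the bleed itself caused the drug to be stopped, the midpoint falls beyond last dose + 2 days in about 48% of cases, wrongly dropping the bleed from the scope.

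**The case against.** The strongest reply is that there may be no cases. Myocardial infarction, stroke, hospitalized limb ischemia and major amputation all go to adjudication with supporting documents, as do potential major bleeds. An event whose year is unknown is improbable, and the 1 to 10 used above is an assumption. This stands, and it is why the point is minor.

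Supportive analyses also limit the damage. TIMI major bleeding is repeated under the ITT scope and the overall study duration (SAP 6.4.5), neither of which depends on the on-treatment label. The primary outcome is repeated over the overall duration (SAP 6.2.10), which does not depend on the ECOD. This stands too, but neither analysis corrects the main on-treatment estimate or the landmark periods.

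For bleeds, the SAP date may be meant as worst-case and never loses a treated patient's bleed, whereas a bare midpoint can. That is a fair point, but SAP 6.4.1 states a worst-case approach only for adverse events with missing dates, and it could not explain the efficacy rule.

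The midpoint is itself arbitrary when a patient is reached only through relatives or once at study end, which protocol 6.3.1 allows; the simulation, with every visit attended, does not cover this. Even then the midpoint respects the known contact dates.

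Finally, section 7 lists the rules openly, and its statement about unchanged analyses compares with SAP version 2.0. So this is an undeclared departure, not a concealed one.

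**Conclusion.** The concern holds and is minor. The protocol and SAP give different dates for the same fully undated non-fatal event, and section 7 does not identify the difference as a departure. The primary hazard ratio is essentially unaffected: under balanced missingness and 1 to 10 undated events, the shift is at most 0.0012 in 97.5% of simulated trials. What is exposed is the exploratory landmark results, the early Kaplan-Meier curve (0.01 to 0.14 percentage points at 3 months) and the on-treatment label of undated bleeds. These sizes rest on the assumed number of events, full visit attendance and the two hazard shapes. The partial-date rules are not in question. The undated-death rule also differs from the midpoint, but its date lies inside the protocol's window and the effect is negligible.

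**What to change.** In SAP 4.3, for a non-fatal event with a completely missing date:

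- Replace the day after randomization with the protocol midpoint: halfway between the last contact known to be event-free and the first contact at which the event was known, and not before randomization + 1 day.
- Assign the ITT, on-treatment and landmark windows from that date.
- For undated bleeds, either keep in the on-treatment scope any bleed recorded as the reason for stopping study drug, or state that the worst-case approach of SAP 6.4.1 extends to bleeds.
- Report the number of fully imputed dates by arm.
- If the undated-death rule is kept, declare it in section 7 as a departure from the protocol.

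The cost is SAP wording and a small programming change. Two derived dates per undated event must be defined. The contacts they need already feed the last clinical event ascertainment date in Appendix A, and reasons for discontinuation are already collected (SAP 4.2), so no new data are required.
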